4 DATABASE LOCK

The primary analysis is planned when the last patient randomized reaches Day 29 (or planned Day 29 if the patient is discharged or leaves the study early). Final analysis will be performed at study end (ie, Day 60).

5 SOFTWARE DOCUMENTATION

All summaries and statistical analyses will be generated using SAS version 9.2 or higher.

6 REFERENCES

Not applicable.

7 LIST OF APPENDICES

Appendix A: Potentially clinically significant abnormalities (PCSA) criteria

Appendix B: Visit Windows based on day ranges

Appendix C: AESI and search criteria

Appendix A Potentially clinically significant abnormalities criteria

CRITERIA for POTENTIALLY CLINICALLY SIGNIFICANT ABNORMALITIES

for phase 2/3 studies (oncology excepted)

(From BTD-009536 “ Analysis and reporting of safety data from clinical trials through the Clinical Study Report” – Version 3 – 21-MAY-2014)

Parameter	PCSA	Comments
Clinical Chemistry		
ALT	By distribution analysis: >3 ULN >5 ULN >10 ULN >20 ULN Additional analysis*: >1 – 1.5 ULN >1.5 – 3 ULN >3 - 5 ULN >5 – 8 ULN > 8 ULN	Enzymes activities must be expressed in ULN, not in IU/L. Concept paper on DILI – FDA draft Guidance Oct 2007. Internal DILI WG Oct 2008. Categories are cumulative. First row is mandatory. Rows following one mentioning zero can be deleted.
AST	By distribution analysis: >3 ULN >5 ULN >10 ULN >20 ULN Additional analysis*: >1 – 1.5 ULN >1.5 – 3 ULN >3 - 5 ULN >5 – 8 ULN > 8 ULN	Enzymes activities must be expressed in ULN, not in IU/L. Concept paper on DILI – FDA draft Guidance Oct 2007. Internal DILI WG Oct 2008. Categories are cumulative First row is mandatory. Rows following one mentioning zero can be deleted.
Alkaline Phosphatase	>1.5 ULN	Enzymes activities must be expressed in ULN, not in IU/L. Concept paper on DILI – FDA draft Guidance Oct 2007. Internal DILI WG Oct 2008.

CRITERIA for POTENTIALLY CLINICALLY SIGNIFICANT ABNORMALITIES

for phase 2/3 studies (oncology excepted)

(From BTD-009536 “ Analysis and reporting of safety data from clinical trials through the Clinical Study Report”– Version 3 – 21-MAY-2014)

Parameter	PCSA	Comments
Total Bilirubin	>1.5 ULN >2 ULN	Must be expressed in ULN, not in µmol/L or mg/L. Concept paper on DILI – FDA draft Guidance Oct 2007. Internal DILI WG Oct 2008. Categories are cumulative. First row is mandatory. Rows following one mentioning zero can be deleted.
Conjugated Bilirubin	>35% Total Bilirubin and TBILI>1.5 ULN Additional analysis*: >1.5 ULN >2 ULN	Conjugated bilirubin dosed on a case-by-case basis. PCSA to be retrieved manually
Unconjugated bilirubin	Additional analysis*: >1.5 ULN >2 ULN	Must be expressed in ULN, not in µmol/L or mg/L. Categories are cumulative.
ALT and Total Bilirubin	ALT>3 ULN and TBILI>2 ULN	Concept paper on DILI – FDA draft Guidance Oct 2007. Internal DILI WG Oct 2008. To be counted within a same treatment phase, whatever the interval between measurement.
CPK**	>3 ULN >10 ULN	FDA Feb 2005. Am J Cardiol April 2006. Categories are cumulative. First row is mandatory. Rows following one mentioning zero can be deleted.
Creatinine	≥150 µmol/L (Adults) ≥30% change from baseline ≥100% change from baseline	Benichou C., 1994.

CRITERIA for POTENTIALLY CLINICALLY SIGNIFICANT ABNORMALITIES

for phase 2/3 studies (oncology excepted)

(From BTD-009536 “ Analysis and reporting of safety data from clinical trials through the Clinical Study Report”– Version 3 – 21-MAY-2014)

Parameter	PCSA	Comments
CLcr (mL/min)	<15 (end stage renal disease)	FDA draft Guidance 2010
(Estimated creatinine clearance based on the Cockcroft-Gault equation)	≥15 - <30 (severe decrease in GFR) ≥30 - < 60 (moderate decrease in GFR) ≥60 - <90 (mild decrease in GFR) ≥ 90 (normal GFR)	Pharmacokinetics in patients with impaired renal function-study design, data analysis, and impact on dosing and labeling
eGFR** (mL/min/1.73m ²)	<15 (end stage renal disease)	FDA draft Guidance 2010
(Estimate of GFR based on an MDRD equation)	≥15 - <30 (severe decrease in GFR) ≥30 - < 60 (moderate decrease in GFR) ≥60 - <90 (mild decrease in GFR) ≥ 90 (normal GFR)	Pharmacokinetics in patients with impaired renal function-study design, data analysis, and impact on dosing and labeling
Uric Acid		Harrison- Principles of internal Medicine 17 th Ed., 2008.
Hyperuricemia	>408 µmol/L	
Hypouricemia	<120 µmol/L	
Blood Urea Nitrogen	≥17 mmol/L	
Chloride	<80 mmol/L >115 mmol/L	
Sodium	≤129 mmol/L ≥160 mmol/L	
Potassium	<3 mmol/L ≥5.5 mmol/L	FDA Feb 2005.
Total Cholesterol	≥7.74 mmol/L ≥6.2 mmol/L*	Threshold for therapeutic intervention.
LDL	≥4.1 mmol/L* ≥4.9 mmol/L	
Triglycerides	≥4.6 mmol/L ≥5.6 mmol/L*	Threshold for therapeutic intervention.
Lipasemia**	≥3 ULN	
Amylasemia**	≥3 ULN	

CRITERIA for POTENTIALLY CLINICALLY SIGNIFICANT ABNORMALITIES

for phase 2/3 studies (oncology excepted)

(From BTD-009536 “ Analysis and reporting of safety data from clinical trials through the Clinical Study Report” – Version 3 – 21-MAY-2014)

Parameter	PCSA	Comments
Glucose		
Hypoglycaemia	≤3.9 mmol/L and <LLN	ADA May 2005.
Hyperglycaemia	≥11.1 mmol/L (unfasted); ≥7 mmol/L (fasted)	ADA Jan 2008.
HbA1c	>8%	
Albumin	≤25 g/L	
CRP	>2 ULN or >10 mg/L (if ULN not provided)	FDA Sept 2005.
Hematology		
WBC	<3.0 Giga/L (Non-Black); <2.0 Giga/L (Black) ≥16.0 Giga/L	Increase in WBC: not relevant. To be interpreted only if no differential count available.
Lymphocytes	<0.5 Giga/L* ≥0.5 Giga/L - LLN* >4.0 Giga/L	
Neutrophils	<1.5 Giga/L (Non-Black); <1.0 Giga/L (Black) <1.0 Giga/L*	International Consensus meeting on drug-induced blood cytopenias, 1991. FDA criteria.
Monocytes	>0.7 Giga/L	
Basophils	>0.1 Giga/L	
Eosinophils	>0.5 Giga/L or >ULN (if ULN ≥0.5 Giga/L)	Harrison- Principles of internal Medicine 17 th Ed., 2008.
Hemoglobin	≤115 g/L (Male); ≤95 g/L (Female) ≥185 g/L (Male); ≥165 g/L (Female) Decrease from Baseline ≥20 g/L	Criteria based upon decrease from baseline are more relevant than based on absolute value. Other categories for decrease from baseline can be used (≥30 g/L, ≥40 g/L, ≥50 g/L).
Hematocrit	≤0.37 v/v (Male) ; ≤0.32 v/v (Female) ≥0.55 v/v (Male) ; ≥0.5 v/v (Female)	

CRITERIA for POTENTIALLY CLINICALLY SIGNIFICANT ABNORMALITIES

for phase 2/3 studies (oncology excepted)

(From BTD-009536 " Analysis and reporting of safety data from clinical trials through the Clinical Study Report" – Version 3 – 21-MAY-2014)

Parameter	PCSA	Comments
RBC	≥6 Tera/L	Unless specifically required for particular drug development, the analysis is redundant with that of Hb. Otherwise, consider FDA criteria.
Platelets	< 50 Giga/L* ≥ 50 - 100 Giga/L* ≥700 Giga/L	International Consensus meeting on drug-induced blood cytopenias, 1991.
Urinalysis		
pH	≤4.6 ≥8	
Vital signs		
HR	≤50 bpm and decrease from baseline ≥20 bpm ≥120 bpm and increase from baseline ≥20 bpm	To be applied for all positions (including missing) except STANDING.
SBP	≤95 mmHg and decrease from baseline ≥20mmHg ≥160 mmHg and increase from baseline ≥20 mmHg	To be applied for all positions (including missing) except STANDING.
DBP	≤45 mmHg and decrease from baseline ≥10 mmHg ≥110 mmHg and increase from baseline ≥10 mmHg	To be applied for all positions (including missing) except STANDING.
Orthostatic Hypotension		
Orthostatic SDB		
Orthostatic DBP	≤-20 mmHg ≤-10 mmHg	
Weight	≥5% increase from baseline ≥5% decrease from baseline	FDA Feb 2007.

Appendix B Visit windows based on day ranges

Table 4 – Time window for lab summaries

Visit Label	Target Day	Hematology, Chemistry	Bacterial infection testing
Daily follow-up until hospital discharge or Day 29			
Baseline	1	≤1	
Day 4	4	2-5	
Day 7	7	6-10	2-10
Day 15	15	11-17	≥11
Day 21	21	18-24	
Day 29	29	≥25	

Appendix C AEsIs and search criteria

Table 5 – AEsIs and search criteria

AESI flag	Search^a criteria
Grade ≥2 infusion related reactions	Any Grade ≥2 (moderate) TEAE of infusion related reactions within 24 hours from the start of study drug infusion based upon CRF checkbox: Infusion Reaction and Yes to AESI event and Severity Grade ≥2.
Grade ≥2 hypersensitivity reactions	SMQ: Anaphylactic reaction, Hypersensitivity or Angioedema and Grade ≥2 (moderate)
Grade 4 neutropenia	ANC <500/mm ³ and CRF checkbox: Yes to AESI event
Grade 4 neutropenia with concurrent invasive infection ^b	ANC <500/mm ³ and Primary SOC: Infections and infestations within 1 week of ANC <500/mm ³
Invasive bacterial or fungal infection ^c	Primary SOC: Infections and infestations
Alanine transaminase (ALT) increase	CRF checkbox: ALT Increase and Yes to AESI event
Overdose ^d	CRF checkbox: Symptomatic overdose

TEAE: Treatment-emergent adverse event

a All SMQs are narrow search

b Patients having both a Grade 4 Neutropenia and a concurrent infection event will be further reviewed by the medical team to confirm that the infection event is invasive.

c Patients identified as having an infection event will be further reviewed by the medical team to confirm that the infection is invasive.

d Standard AESI applies to all Sanofi studies

Signature Page for VV-CLIN-0581573 v3.0
efc16844-16-1-9-sap

Approve & eSign	[Redacted] Clinical [Redacted]
-----------------	--------------------------------------

Approve & eSign	[Redacted] [Redacted]
-----------------	--------------------------

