### 8.3.6 Adverse event of special interest

#### Adverse event of special interest

An adverse event of special interest (AESI) is an AE (serious or nonserious) of scientific and medical concern specific to the Sponsor's product or program, for which ongoing monitoring and immediate notification by the Investigator to the Sponsor is required. Such events may require further investigation in order to characterize and understand them. Adverse events of special interest may be added, modified or removed during a study by protocol amendment.

The AESI require reporting to the sponsor (or designee) within 24 hours of learning of the event:

- **Adverse Events of Special Interest (AESI; serious and nonserious) include the following:**
  - Grade  $\geq 2$  infusion related reactions (Infusion related reactions are defined as any signs or symptoms experienced by patients who receive IMP within 24 hours of the start of infusion)
  - Grade  $\geq 2$  hypersensitivity reactions
  - Grade 4 neutropenia ( $ANC < 500/\text{mm}^3$ )
  - Grade 4 neutropenia with concurrent invasive infection ( $ANC < 500/\text{mm}^3$ )
  - Increase in alanine transaminase (ALT)  $\geq 3X \text{ ULN}$  (for patients with normal baseline) or  $> 3X \text{ ULN}$  AND at least 2-fold increase from baseline value (for patients with abnormal baseline)
  - Invasive bacterial or fungal infections of clinical significance with confirmed diagnosis based on the Investigator's assessment with appropriate diagnostic workups and consultations
  - Symptomatic overdose (serious or nonserious) with IMP
    - An overdose (accidental or intentional) with the IMP is an event suspected by the Investigator or spontaneously notified by the participant (not based on systematic pills count) and defined as an increase of at least 30% of the dose to be administered in the specified duration or if the dose is administered in less than half the recommended duration of administration.

Management of acute reactions is described in [Section 10.3.4](#).

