#### **Events meeting the AE definition**

- “Lack of efficacy” or “failure of expected pharmacological action” per se will not be reported as an AE or SAE. Such instances will be captured in the efficacy assessments. However, the signs, symptoms, and/or clinical sequelae resulting from lack of efficacy will be reported as AE or SAE if they fulfil the definition of an AE or SAE.
- Any abnormal laboratory test results (hematology, clinical chemistry, or urinalysis) or other safety assessments (eg, ECG, radiological scans, vital signs measurements), including those that worsen from baseline, considered clinically significant in the medical and scientific judgment of the Investigator (ie, not related to progression of underlying disease), eg:
  - Requiring either corrective treatment or consultation, and/or
  - Leading to IMP discontinuation or modification of dosing, and/or
  - Fulfilling a seriousness criterion, and/or
  - Defined as an AESI
- Exacerbation of a chronic or intermittent pre-existing condition including either an increase in frequency and/or intensity of the condition.
- New conditions detected or diagnosed after study intervention administration even though it may have been present before the start of the study.
- Signs, symptoms, or the clinical sequelae of a suspected drug-drug interaction.
- Signs, symptoms, or the clinical sequelae of a suspected overdose of either study intervention or a concomitant medication.

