#### **Events NOT meeting the AE definition**

- Any clinically significant abnormal laboratory findings or other abnormal safety assessments which are associated with the underlying disease, unless judged by the Investigator to be more severe than expected for the participant’s condition.

- The disease/disorder being studied or expected progression, signs, or symptoms of the disease/disorder being studied, unless more severe than expected for the participant's condition.
- Medical or surgical procedure (eg, endoscopy, appendectomy): the condition that leads to the procedure is the AE.
- Situations in which an untoward medical occurrence did not occur (social and/or convenience admission to a hospital).
- Anticipated day-to-day fluctuations of pre-existing disease(s) or condition(s) present or detected at the start of the study that do not worsen

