1.2.2 Secondary objectives

- Evaluate the 28-day survival rate
- Evaluate the clinical efficacy of sarilumab compared to the control arm by clinical severity
- Evaluate changes in the National Early Warning Score 2 (NEWS2)
- Evaluate the duration of predefined symptoms and signs (if applicable)
- Evaluate the duration of supplemental oxygen dependency (if applicable)
- Evaluate the incidence of new mechanical ventilation use during the study
- Evaluate the duration of new mechanical ventilation use during the Study
- Evaluate the proportion of patients requiring rescue medication during the 28-day period
- Evaluate need for admission into intensive care unit (ICU)
- Evaluate duration of hospitalization (days)
- The secondary safety objectives of the study are to evaluate the safety of sarilumab through hospitalization (up to Day 29 if patient is still hospitalized) compared to the control arm as assessed by incidence of:
 - Serious adverse events (SAEs)
 - Major or opportunistic bacterial or fungal infections in patients with grade 4 neutropenia
 - Grade ≥ 2 infusion related reactions
 - Grade ≥ 2 hypersensitivity reactions
 - Increase in alanine transaminase (ALT) $\geq 3X$ ULN (for patients with normal baseline) or $>3X$ ULN and at least 2-fold increase from baseline value (for patients with abnormal baseline)
 - Major or opportunistic bacterial or fungal infections

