2.1.4.1 Adverse events variables

Adverse event observation period

- Pre-treatment AEs are AEs that developed or worsened or became serious from the signed informed consent date up to first administration of IMP
- TEAEs are AEs that developed or worsened or became serious during the TEAE period
- Post-treatment AEs are AEs that developed or worsened or became serious during the post-treatment period

All AEs (including SAEs and AESIs) will be coded to a “LLT”, “PT”, “HLT”, “HLGT”, and associated primary “SOC” using the version of MedDRA currently in effect at Sanofi at the time of database lock.

The occurrence of AEs (including SAEs and AESIs) will be recorded from the time of signed informed consent until the end of the study.

Adverse events of special interest (AESI; serious and nonserious) include the following:

- Grade ≥ 2 infusion related reactions (Infusion related reactions are defined as any signs or symptoms experienced by patients who receive IMP within 24 hours of the start of infusion)
- Grade ≥ 2 hypersensitivity reactions
- Grade 4 neutropenia ($ANC < 500/mm^3$)

- Grade 4 neutropenia with concurrent invasive infection (ANC<500/mm³)
- Increase in alanine transaminase (ALT) $\geq 3X$ ULN (for patients with normal baseline) or $>3X$ ULN AND at least 2-fold increase from baseline value (for patients with abnormal baseline)
- Invasive bacterial or fungal infections of clinical significance with confirmed diagnosis based on the Investigator's assessment with appropriate diagnostic workups and consultations
- Symptomatic overdose (serious or nonserious) with IMP
 - An overdose (accidental or intentional) with the IMP is an event suspected by the Investigator or spontaneously notified by the participant (not based on systematic pills count) and defined as an increase of at least 30% of the dose to be administered in the specified duration or if the dose is administered in less than half the recommended duration of administration.

AESIs will be flagged in the database using search criteria. All AEs captured on the general AE form, the ALT increase form, infusion reaction symptoms form, and the infection event form will be searched. The list of search criteria is provided in [Appendix C](#).

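### SAP Appendix C flags Grade 4 neutropenia and ALT increase by rules that do not match their AESI definitions: a tick-box is added to the first and is the only test for the second

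*SAP*

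**What the plan says.** Protocol 8.3.6 and SAP 2.1.4.1 give the same definitions. Grade 4 neutropenia is an ANC below 500/mm³, with no further condition. ALT increase is at least 3 x ULN when baseline is normal; otherwise it is above 3 x ULN "AND at least 2-fold increase from baseline value (for patients with abnormal baseline"). SAP 1.2.2 repeats the ALT rule as a secondary safety objective, including the "at least 2-fold increase from baseline value (for patients with abnormal baseline") condition.

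SAP 2.1.4.1 then says that AESIs are flagged by search criteria, and names the sources: "All AEs captured on the general AE form, the ALT increase form, infusion reaction symptoms form, and the infection event form will be searched". Laboratory data are not named.

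The criteria in Appendix C Table 5 are:
- Grade 4 neutropenia: ANC below 500/mm³ "and CRF checkbox: Yes to AESI event".
- Grade 4 neutropenia with concurrent invasive infection: ANC below 500/mm³ and "Primary SOC: Infections and infestations within 1 week of ANC" below 500/mm³. No box is needed; a footnote adds medical review of whether the infection is invasive.
- ALT increase: "CRF checkbox: ALT Increase and Yes to AESI event". No laboratory value enters.

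**The concern.** The table that produces the AESI counts does not apply the definitions that the same SAP states. For ALT the threshold is absent. For neutropenia it is present but narrowed by a second condition.

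The box would be harmless if it always followed the laboratory value, but the protocol leaves room for it not to. Protocol 10.3.1 lists "Defined as an AESI" among the reasons to report an abnormal laboratory result. The same section excludes "Any clinically significant abnormal laboratory findings or other abnormal safety assessments which are associated with the underlying disease", unless the finding is more severe than expected. In COVID-19, two sites could treat the same ALT rise differently. The SAP states no check of boxes against values.

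At stake are one secondary safety objective (ALT) and one AESI of a drug that protocol 2.3 expects to lower ANC rapidly.

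**Working it through.** No figure in the plan needs reproducing. The check compares rules and thresholds.

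**1. Neutropenia.** Take three yes/no facts: ANC below 500, box ticked, infection within a week.
- Definition = ANC below 500.
- Table 5 Grade 4 row = ANC below 500 and box.
- Table 5 infection row, before medical review = ANC below 500 and infection.

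Of the 8 combinations, 2 disagree with the definition, both with ANC below 500 and no tick. Both are omissions, so the row can only under-count. In one of the two (infection present) the patient can enter the infection row but not the Grade 4 row, so the rows do not nest.

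**2. ALT.** Take two facts: laboratory criterion met, boxes ticked. The Table 5 flag equals the boxes. Of the 4 combinations, 2 disagree: met but not ticked (missed), and ticked but not met (counted wrongly). The error can go either way.

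**3. Does the laboratory table stand in for ALT?** SAP Appendix A has rows for potentially clinically significant abnormalities (PCSAs) at >3, >5, >10 and >20 ULN, independent of any box. With baseline B in multiples of ULN and normal taken as B ≤ 1, the AESI threshold is 3 for B ≤ 1 and max(3, 2B) otherwise. Protocol exclusion E 02 allows screening ALT up to 5 x ULN.

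| B | AESI threshold | Values in the >3 ULN row that are not AESIs | Baseline status for that row |
|---|---|---|---|
| up to 1 | 3 | none | normal |
| 1.5 | 3 | none | normal |
| 2 | 4 | above 3, below 4 | normal |
| 2.5 | 5 | above 3, below 5 | normal |
| 3 | 6 | above 3, below 6 | normal |
| 4 | 8 | above 3, below 8 | abnormal |
| 5 | 10 | above 3, below 10 | abnormal |

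The >3 ULN row misses only a value of exactly 3.0 x ULN with a normal baseline. It over-counts whenever B exceeds 1.5. The planned split by baseline PCSA status does not remove this, because baselines from 1.5 to 3 x ULN count as normal for this row. The >5 ULN row over-counts only for B above 2.5. The >10 and >20 rows do not over-count for B up to 5.

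**4. Does the laboratory table stand in for ANC?** The lowest neutrophil cut in Appendix A is <1.0 Giga/L, that is 1000/mm³. In protocol Table 14 that cut merges Grade 3 (500 to below 1000) with Grade 4 (below 500). By-visit summaries can show some low minima, but SAP 2.5.4 keeps one value per window and prefers scheduled ones. Protocol 9.4.5.2 plans listings that flag out-of-range values, so low ANCs are visible but not tabulated. No planned table counts all ANC below 500 from laboratory data alone.

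**5. Size.** The documents give neither incidence nor box completeness. By assumption only, in an arm of 160:
- True incidence 5%: 160 × 0.05 = 8.0 expected patients; 8.0 × 0.9 = 7.2 flagged at 90% completeness and 8.0 × 0.7 = 5.6 at 70%.
- True incidence 10%: 16.0 expected; 14.4 and 11.2 flagged.

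At the arm sizes in SAP 1.3, one patient is 100/160 = 0.63 or 100/80 = 1.25 percentage points. Amendment 04 closed the 200 mg arm to enrolment, so actual sizes will differ.

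**6. A minor separate point.** SAP 2.4.5.3 says that haematology, chemistry and urinalysis are local, and orders an 'endpoint' summary for them. The only definition, in SAP 2.4.5, is for central measurements and takes the value at the last dose or the closest earlier one. Protocol 1.3 (footnotes 2 and 6) has baseline and second-dose samples drawn before dosing. If borrowed, the definition therefore normally returns baseline for single-dose patients (change = 0) and the pre-second-dose value for the others.

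**The case against.** The best defence is that an AESI is an adverse event, not a laboratory endpoint. Protocol 9.4.3.2.1 plans AESI summaries by preferred term or prespecified grouping, and protocol 8.3.6 requires reporting within 24 hours. Protocol 8.2.4 requires investigators to review every laboratory report, a dedicated ALT form exists, and protocol 10.3.2.1 gives follow-up guidance for exactly these two AESIs. On this view the box carries the investigator's application of the definition, and laboratory abnormalities have their own analysis.

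Much of this stands. A Grade 4 neutropenia reported without a tick still appears in the treatment-emergent table by CTC grade. An unticked ALT event still appears in the separate ALT-increase summary, for which SAP 2.4.5.1 states no AESI-box condition. Those tables cover the plainest failure of a box condition. They do not cover a crossing never reported as an adverse event, or a ticked ALT event below threshold. Nor does the defence explain why one neutropenia row needs the box and its own subset does not.

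Three stronger readings are tempting. A reader might infer that Appendix C ignores the laboratory definition of Grade 4 neutropenia; it does not, since the ANC limit is in the row. A reader might infer that boxes and values will in fact diverge; the CRF, its instructions and its edit checks are not in the documents, so this cannot be known. And because AESI imbalance is a listed ground for discontinuing an arm (protocol 7.2 and 9.6), a reader might infer that safety monitoring was compromised; the committee's outputs are not shown, so that does not follow either.

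**Conclusion.** The mismatch is real and lies in the text. Followed literally, Table 5 can under-count Grade 4 neutropenia, can produce an infection subset that is not contained in its parent row, and can misstate ALT increase in either direction. No planned table derives ALT increase by its stated definition from laboratory values, although it is a secondary safety objective.

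The consequence is limited. The tables are descriptive, and no hypothesis test or alpha is touched. Other adverse-event tables, the ALT PCSA rows and the laboratory listings recover most of the information. The size of the residual error is unknown. The conclusion rests on reading Table 5 as the operative rule, as SAP 2.1.4.1 says, and on no unseen edit check forcing agreement between box and value. The 'endpoint' row is a clarification that affects one summary row; every post-baseline visit is still summarised.

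**What to change.** - In Appendix C, flag Grade 4 neutropenia from any on-treatment ANC below 500/mm³, with no box condition. Keep the medical review for the infection row, which will then nest.
- Flag ALT increase by the thresholds in protocol 8.3.6 and SAP 2.1.4.1, including the 2-fold rule, against the last pre-dose value. Treat a missing baseline as normal, as SAP 2.5.3 already does for PCSAs.
- Name the laboratory data among the sources in SAP 2.1.4.1.
- Show investigator-ticked events beside the laboratory-derived counts rather than merging them, and reconcile discordant cases before database lock.
- Add a <0.5 Giga/L row to the neutrophil PCSA criteria.
- Separately, in SAP 2.4.5.3 define 'endpoint' for local tests as the last on-treatment value after the first dose, or delete the row.

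The cost is SAP wording and a little programming on data already collected. The downside is some site queries and possibly slightly higher laboratory-derived counts, including isolated values that the investigator did not report.
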